1. SUMMARY OF THE STUDY

1.1 Background and Justification

Neurodevelopmental challenges (DNDs) affect approximately 15% of infants and adolescents worldwide, producing significant impairment in cognition, communication, adaptive behavior, and psychomotor skills. Autism spectrum (ASD) has an estimated global prevalence of 0.77%, with higher rates among males.

In Argentina, a DND rate of 20% has been reported through screening methods. Adaptive behavior, defined as the conceptual, social, and practical skills needed to function in the everyday environment, is a fundamental predictor of future quality of life and can be modified through specific evidence-based interventions.

The study aims to know the impact of the Sentido® Model on the gain of adaptive behaviors, which is important for five fundamental reasons:

1. **To improve the quality of life** of infants, families and professionals who live with neurodevelopmental challenges.
2. **Inform parents** about the efficacy and effectiveness of the interventions offered.
3. **Provide evidence** for government agencies, public and private policymakers, prepaid, and health insurance companies.
4. **Contribute** with a manualized intervention program that is contextually appropriate to the strengths and challenges of a low- and middle-income country.
5. **Provide evidence-based data** on whether the programs created fit the population needs and cultural particularities of the region.

1.2 Description of the Sentido's® Model

The Sentido's Model (SM) is an innovative proposal for the understanding and intervention of DNDs, epistemologically based on a transcomplex perspective that integrates the postulates of Morín (1996) complex thinking with Nicolescu's (1996; 2025) transdisciplinarity.

Evidence-Based Frameworks:

1. **Applied Behavior Analysis (ABA):** Interventions with extensive empirical support, recognized as evidence-based practice for ASD and DND (Hagopian *et al.*, 2015).
2. **Ayres Sensory Integration (ASI):** Validated practice for children in ASD aged 4-12 years (Schoen *et al.*, 2019).
3. **Psychoimmunoneuroendocrinology (PINE):** Stress medicine approach during critical periods of neurodevelopment (Danese & Lewis, 2017).

Operational Structure of the Sentido's® Model:

MS is a model that integrates diverse frameworks and paradigms for the intervention of children in ASD and other related DNDs, their significant caregivers and intervening therapists. To achieve this purpose, it is based on a transcomplex perspective that seeks

practical actions of a **science with consciousness** and materializes a multidimensional bio-neuro-sensory-psycho-social-spiritual-occupational-nutritional-ecological approach structured in a hierarchical architecture of four interrelated operational components.

1. NINE INTEGRATED DIMENSIONS (multidimensional framework): MS encompasses nine dimensions for comprehensive understanding, reasoning, and intervention:

Biological Dimension: Biological evolution accounts for how human behavior and genetics impact the way we act; it studies the morphophysiology and behavior of organic structures; it includes epigenetic regulation that allows the formation of different phenotypes depending on the environment.

Neurological Dimension: Examines the neurobiological aspects and functioning of the central nervous system in human development.

Sensory Dimension: The sensory processing of the central nervous system, especially the vestibular, proprioceptive, and tactile senses that impact adaptive behavior.

Psychological Dimension: The cognitive, emotional, and mental processing aspects of development.

Social Dimension: The social interactions, family dynamics, and relational contexts that influence development.

Spiritual Dimension: Integrates concepts such as ikigai (life purpose) and belief systems as therapeutic resources for psychological well-being and vital meaning.

Occupational Dimension: The systematic study of human behavior from children's play to adult work; the daily and family activities that influence health and well-being.

Nutritional Dimension: Neuronutrition as a science that links food to health and disease; it studies how nutrients affect the nervous system, behavior, and cognition.

Ecological Dimension: The study of the relationship between organisms and their environment; it includes factors such as screen time, physical activity, parental care, and social interactions that influence development.

2. SIX FUNDAMENTAL PREMISES (conceptual principles):

1. **Behavioral Premise**, which evaluates how the child and the family behave, constituting the diagnostic entry point by observing behavioral patterns and relational dynamics.

2. **Genetic/Epigenetic Imprinting premise**, which examines how genetics influences observed behavior, recognizing that family practices can modulate gene expression.

3. **Organic Condition Premise**, which identifies which medical conditions of the child (allergies, gastrointestinal disorders, sleep disturbances) impact their behavior and family functioning.

4. **Sensory Profile Premise**, which assesses how the central nervous system processes sensory information and how the family responds to these manifestations.

5. **Environmental Premise**, which analyzes how environmental, family, and social factors influence the child's development.

6. **Premise of Belief Systems and Spirituality**, which integrates spiritual strengths as therapeutic resources for the family to find meaning in the process of accompanying the child's development, generating deep and lasting systemic transformations.

3. THREE THEORETICAL POSTULATES (theoretical bases):

1. **Postulate of Neurobehavior** - Human behavior is the observable manifestation of how the central nervous system processes and integrates sensory information from the body and environment, where alterations in these processes are expressed as atypical behavioral patterns.

2. **Postulate of the Function of Behaviors** - All behavior fulfills a specific adaptive function and constitutes operant responses controlled by contingencies of three terms (antecedent-behavior-consequence) that can be identified and modified by functional analysis.

3. **Postulate of the Possibility of Conditioning Unhealthy Responses** - Maladaptive responses and problem behaviors are manifestations of alterations in the psychoneuroimmunoendocrine systems that can be modified by interventions that modulate the activation of the hypothalamic-pituitary-adrenal axis and the autonomic nervous system during critical periods of development.

4. THREE INTEGRATED STRATA (levels of intervention):

Stratum I: Childhoods in ASD and other associated DNDs - The central core that encompasses childhoods with autism spectrum characteristics and other neurodevelopmental challenges, focusing on teaching strategies to gain adaptive skills.

Stratum II: Meaningful Caregivers – Parents and caregivers, recognizing that child development occurs within family systems where caregivers' responsiveness is critical to adaptive functioning.

Stratum III: Therapists (Professionals) Involved - The health and education professionals who implement the model, requiring specialized training and interdisciplinary and transdisciplinary collaborative work.

This operational structure reflects the complexity and conceptual richness of the Sentido Model,[®] providing the complete theoretical framework that supports the entire transcomplex intervention methodology. In order to teach infants to use strategies that contribute to the gain of adaptive behaviors/skills through a guided, organized, and systematic process, evidence-based, and goal-driven by goals that families consider meaningful to achieve greater well-being in children's daily lives and family dynamics, considering the holistic integration of the nine dimensions, based on the six premises and the three theoretical postulates.

2. OBJECTIVES

2.1 Main Objective

To describe the impact of the Sentido® Model on the adaptive behaviors of children between 3 and 7 years old, on the autism spectrum and other associated neurodevelopmental challenges, who attend the Sentido's Therapeutic Organization, during a period of 17 weeks.

2.2 Secondary Objectives

1. Implement the syllabus protocol and MS programs in participating families
2. Apply protocols in children between 3-7 years of age with associated ASD and DND
3. Evaluate agreed goals using Goal Attainment Scaling (GAS) at three time points
4. Identify domains and subdomains of acquired adaptive behaviors
5. To analyze results of the Family Outcome Survey (FOS) in significant caregivers
6. Perform comprehensive statistical analysis of the results obtained

3. HYPOTHESIS

The Sentido's® Model provides tools that promote and develop adaptive behaviors in children in the AE and other associated DNDs, simultaneously enhancing the competencies, confidence and care skills of families towards their children.

4. STUDY DESIGN

4.1 Type of Study

Prospective longitudinal intervention study, pretest-posttest design with follow-up. Non-concurrent single-subject design, multiple baseline, repeated measures between subjects.

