4.2 Design Justification

This design constitutes a useful first step in the research of treatment efficacy, seeking to establish a relationship between individualized intervention and change in expected results. The subject acts as his or her own control, comparing performance before, during, and after the intervention.

The non-concurrent design offers greater flexibility in clinical settings by not requiring concurrent collection of baseline data. When replicated with multiple subjects, it provides a systematic and cost-effective method for replicating results.

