9. STUDY PROCEDURES

9.1 Sampling Periods

Phase 1 - PRE-TEST (Baseline - Week 0):

- Control period during therapeutic admission.
- Vineland-3 administration, FOS to significant parents/caregivers.
- Elaboration of collaborative GAS objectives (parents-professionals).
- Complete interdisciplinary diagnostic evaluation.

Phase 2 - INTERVENTION (Weeks 1-14):

- Implementation of the Sentido's® Model according to the syllabus protocol.
- 4 weekly sessions of 60 minutes.
- Daily record of progress by professionals.
- Inclusion of caregivers (12 structured sessions), gradual fading of their participation in the sessions.

Phase 3 - POST-TEST (Week 15):

- Re-administration of Vineland-3, FOS, GAS evaluation after 14 weeks of intervention.
- Skills maintenance evaluation.

Phase 4 - FOLLOW-UP (Week 17):

- Third administration Vineland-3.
- Evaluation of GAS (parent-professional) objectives after two weeks without intervention.
- Post-intervention sustainability analysis.
- Return to usual intervention.

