2. STUDY DESIGN AND GENERAL CONSIDERATIONS

2.1 Type of Design

- **Design:** Prospective longitudinal intervention, pretest-posttest with follow-up.
- **Configuration:** Non-concurrent single subject design, multiple baseline.
- **Analysis:** Repeated intra-subject measures with three time points.

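### The multiple-baseline, single-subject label in Protocol 4.1 and SAP 2.1 is not supported by the schedule or the analysis, which describe a single-group pretest-posttest study

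*Combined protocol and SAP*

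**What the plan says.** Protocol 4.1 gives two descriptions. The first is a prospective pretest-posttest intervention study with follow-up. The second reads "Non-concurrent single-subject design, multiple baseline, repeated measures between subjects". SAP 2.1 has the same pair, with "Non-concurrent single subject design, multiple baseline" as the configuration, but calls the repeated measures intra-subject.

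Protocol 4.2 justifies the design as a first step towards relating an individualized intervention to change in outcome. It adds: "The subject acts as his or her own control, comparing performance before, during, and after the intervention". On timing it says: "The non-concurrent design offers greater flexibility in clinical settings by not requiring concurrent collection of baseline data".

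The schedule is in Protocol 9.1. "Phase 1 - PRE-TEST (Baseline - Week 0") contains one administration of Vineland-3 and FOS and the setting of GAS goals. It also lists a "Control period during therapeutic admission". "Phase 2 - INTERVENTION (Weeks 1-14") contains the sessions and a "Daily record of progress by professionals", but none of the three scales. Vineland-3, GAS and FOS follow at week 15, and Vineland-3 and GAS at week 17. SAP 3.1 confirms weeks 0, 15 and 17 for the primary outcome.

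SAP 4.2.1 analyses the primary outcome by a one-factor repeated measures ANOVA on those three occasions. SAP 4.2.2 uses the same method for the Vineland-3 domains and FOS, and Friedman tests for GAS. SAP 10.1 lists the absence of a control group as a limit on causal inference, and practice or time effects as possible.

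**The concern.** A multiple-baseline design draws its inference from two features. Each subject is measured repeatedly before treatment, so that a pre-existing trend can be seen, and treatment starts after baselines of different length, so that change can be tied to the start of treatment rather than to time since entry. In the non-concurrent form the baselines need not share calendar time, but both features are still required. If neither is planned, the label tells a reader that the study has an internal comparison which it does not have.

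This matters because of how the result is to be used. Protocol 2.1 speaks of the Model's impact. Protocol 1.1 wants to inform parents about efficacy and effectiveness and to supply evidence to policymakers and insurers. A reader who stops at 4.1 and 4.2 takes away a stronger design than a reader who reaches SAP 10.1.

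**Working it through.** The plan has no figure to reproduce here: n = 24 in SAP 2.2 comes without a power calculation. The check sets the label against the schedule and the analysis.

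**Step 1. What the label needs and what is planned**

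| Feature | What the documents give |
|---|---|
| Repeated outcome measurement before treatment | One scheduled assessment, week 0 (Protocol 9.1, SAP 3.1) |
| Baselines of differing length | None specified. The control period in 9.1 and the evaluation and probing phase in 6.1.1 have no stated length and no repeated measurement |
| Staggered start | None. Intervention occupies weeks 1-14 for every child (9.1) |
| Outcome data during treatment | No Vineland-3, GAS or FOS in weeks 1-14. The daily record is listed only in that phase and enters no SAP analysis |
| Within-child analysis of level, trend or phase | None. Group ANOVA and Friedman tests only (SAP 4.2.1, 4.2.2, 5.1) |

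**Step 2. What follows**

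- With one pre-treatment point per child, no pre-treatment trend can be estimated.
- With one scheduled start (week 1), time since entry and time since treatment began move together for every child.
- The comparison during treatment promised in 4.2 has no outcome data behind it.
- Between subjects in 4.1 and intra-subject in SAP 2.1 cannot both describe the same three repeated measurements. The ANOVA in SAP 4.2.1 treats time as a within-subject factor, so SAP 2.1 matches the analysis.

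**Step 3. Illustration of having no control group (not the size of the labelling error)**

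Suppose the Model has no effect and all children share a drift of d points over 17 weeks, linear in time.

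Inputs:
- n = 24 (SAP 2.2) and alpha = 0.05 (SAP 4.5.1).
- SD = 15, the norm value in SAP 3.1, assumed for this sample.
- Correlation r between occasions = 0.64 to 0.92, the test-retest range in Protocol 8.1, assumed to apply to the composite and to this interval.
- d = 3, assumed. The documents give no drift.

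Means at weeks 0, 15 and 17: 0, 3 × 15/17 = 2.65, and 3. Their average is 1.88. The sum of squared deviations is 5.38.

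Noncentrality = n × (sum of squares) / [SD² × (1 − r)]:
- r = 0.64: 24 × 5.377 / (225 × 0.36) = 129.05 / 81 = 1.59
- r = 0.92: 24 × 5.377 / (225 × 0.08) = 129.05 / 18 = 7.17

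With 2 and 46 degrees of freedom (critical F = 3.20), the chance of a significant ANOVA is about 18% and 64%. A simulation of 20,000 studies per setting agrees, and returns about 5% at zero drift. A drift of 5 points gives about 43% and 98%.

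For the week 0 versus week 17 comparison taken alone at the Bonferroni level 0.05/3 = 0.0167, and before the requirement of a significant F in SAP Step 3, a 3-point drift gives about 10% and 46%.

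**The case against.** The strongest reply is that the plan already describes itself correctly and admits its limits. Protocol 4.1 and SAP 2.1 both lead with the pretest-posttest label. SAP 1.1 frames the primary objective as change in children who received the intervention. Protocol 4.2 calls the design only a first step, and SAP 10.1 concedes both the missing control group and possible practice or time effects. All of this stands. It makes the defect a contradictory second label with its rationale, not a hidden limitation or a wholly misdescribed study. It does not remove the contradiction: 4.1, 4.2 and SAP 2.1 still carry the stronger label.

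A reader might infer that the documents claim control over maturation. No section says so. Section 4.2 claims only that each child serves as own control and that the design seeks a relationship between intervention and change.

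A baseline of varying length might be hidden in the control period or the probing phase. This cannot be excluded, so the supportable statement is that length and repetition are unspecified, not that every child's baseline was equally long.

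Entry spread over 2024 (Protocol 4.4.3) gives some protection against a single calendar event. It gives none against maturation, repeat testing or regression to the mean, because the timeline from entry is the same for each child. Standard scores, if age-normed, remove average growth in the norm sample. That is a property of the scale, not of the design. SAP 10.2 says the scale is not validated in Argentina, and the argument does not extend to GAS or FOS.

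The daily records might seem to rescue a single-case analysis. They are listed only for the intervention phase, so they supply no baseline.

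**Conclusion.** The point holds as a conflict between the label and the plan. The documents specify one scheduled outcome assessment before treatment, no staggered start, no outcome assessment during treatment and no within-child analysis. They therefore do not support the multiple-baseline, single-subject label in Protocol 4.1 and SAP 2.1, or the comparison during treatment in 4.2. Between subjects in 4.1 also contradicts intra-subject in SAP 2.1. This conclusion rests on the documents alone and needs no assumption.

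It is tempting to read the 18% to 64% as the harm done by the label. It is not. The same chance applies to any single-group pre-post study with these inputs and would be unchanged after relabelling. It illustrates the missing control group, which SAP 10.1 already admits, and it depends on an assumed 3-point drift, the norm SD and the assumed correlation range. A 3-point change is also the lower edge of what SAP 5.2.1 calls minimum change, well below the 15 points it calls clinically significant.

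The planned tests can be run as written. What changes is what the study may say about their result.

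**What to change.** - **Protocol 4.1, 4.2 and SAP 2.1:** delete the multiple-baseline, single-subject and between-subjects wording. State instead: *single-group, uncontrolled pretest-posttest study with one baseline and two post-intervention assessments, within-subject analysis*. This describes the primary outcome; 9.1 lists FOS at weeks 0 and 15 only.
- **Protocol 4.2:** remove the reference to a comparison during the intervention.
- **SAP 5.1, Step 7:** limit the conclusion to *change observed over 17 weeks in children receiving the Model*, in line with SAP 10.1, rather than impact or efficacy.
- **Alternative, only if repeated baselines of differing length were actually collected:** document the number of points, the lengths and how they were set for each child, and add a within-child analysis to the SAP.

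The main fix is wording in the protocol and SAP, with no new visits or data. Its price is a weaker design label and a more modest claim. By the timeline in Protocol 4.4 the study runs in 2023-2025, so adding a stagger now is unlikely to be possible and correcting the label is the realistic course.

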4.2 Design Justification

This design constitutes a useful first step in the research of treatment efficacy, seeking to establish a relationship between individualized intervention and change in expected results. The subject acts as his or her own control, comparing performance before, during, and after the intervention.

The non-concurrent design offers greater flexibility in clinical settings by not requiring concurrent collection of baseline data. When replicated with multiple subjects, it provides a systematic and cost-effective method for replicating results.

4.3 Duration of the Study

- **Recruitment period:** 2023-2024.
- **Duration of individual participation:** 17 weeks.
- **Active intervention:** 14 weeks.
- **Post-intervention follow-up:** 3 weeks (3 weeks without intervention from week 15 to week 17).

4.4 Study timeline

4.4.1 Schedule of general activities

Activities	2023	2024	2025
Update bibliography	✓	✓	✓
Transmit the methodology of the Sentido's Model to the participating professionals	✓	✓	✓
Select Population	✓	✓	✓
Sign consents	✓	✓	✓
Implement the syllabus protocol and the Modelo Sentido's programs in families	✓	✓	✓
Administer the scales: Vineland-3, GAS, FOS	✓	✓	✓
Apply the syllabus protocol and MS programs	✓	✓	✓
Remanage: GAS Scale, FOS Scale, Vineland-3	-	✓	✓
Statistically analyze the results obtained	-	✓	✓
Report Results Achieved	-	-	✓
Thesis writing	-	-	✓

4.4.2 Timeline of the phased study

Phase	Activity	Duration	Responsible
Preparation	Staff Training	4 weeks	PI
Recruitment	Identification and Consent	12 months	Clinical Team

Phase	Activity	Duration	Responsible
Intervention	MS Implementation	14 weeks/participant	Certified Therapists
Tracking	Post-intervention evaluations	3 weeks/participant	Evaluators
Analysis	Statistical analysis and reporting	8 weeks	Biostatistician + PI

4.4.3 Gantt Chart - Integrated Timeline

Legend of Study Phases				
●●●● PREPARATION	●●●● RECRUITMENT	●●●● INTERVENTION	●●●● FOLLOW-UP	●●●● ANALYSIS

Integrated Timeline (2023-2025)

Phase/Activity	2023Q4	2024				2025T1-T3
	Oct-Dec	Jan-Mar	Apr-Jun	Jul-Sep	Oct-Dec	Jan-Sep
PREPARATION	●●●●	-	-	-	-	-
• Professional training	●●●●	-	-	-	-	-
RECRUITMENT	-	●●●●	●●●●	●●●●	●●●●	-
• Participant identification	-	●●●●	●●●●	●●●●	●●●●	-
• Informed consents	-	●●●●	●●●●	●●●●	●●●●	-
INTERVENTION	-	●●●●	●●●●	●●●●	●●●●	●●●●
• Sentido Model App's®	-	●●●●	●●●●	●●●●	●●●●	●●●●

Phase/Activity	2023Q4	2024				2025T1-T3
	Oct-Dec	Jan-Mar	Apr-Jun	Jul-Sep	Oct-Dec	Jan-Sep
• Regular evaluations (Vineland-3, GAS, FOS)	-	••••	••••	••••	••••	••••
TRACKING	-	-	-	-	-	••••
• Post-intervention evaluations	-	-	-	-	-	••••
ANALYSIS	-	-	-	-	-	••••
• Statistical analysis	-	-	-	-	-	••••
• Writing of reports and theses	-	-	-	-	-	••••

Note: The schedule shows the main activities of the study. The recruitment and intervention phases may overlap since a non-concurrent single-subject design is implemented. The estimated total duration of the study is 36 months (2023-2025).

5. PARTICIPANTS

5.1 Target Population

Universe: Children aged 3-7 years with ASD and other associated DNDs who attend Sentido's Therapy Organization CAIP&CICI (Comprehensive Pediatric Care Center and Intensive Behavioral Intervention Center), Comodoro Rivadavia, Chubut, Argentina.

Sample: All eligible childhoods during the study period.

Selection: Non-probabilistic convenience, non-random, voluntary.

